17. PREVIOUS RESPIMAT® SMI USE

Analysis Set: FAS

Information on previous Respimat® use collected on the “Prior Respimat® Use” eCRF page will be summarised for Respimat® SMI-experienced patients cohort subgroups.

For *Respimat® SMI-experienced patients on maintenance treatment with a re-usable Respimat® SMI at study entry* the following will be described:

- Re-usable Respimat® SMI product prescribed prior to study entry: Spiriva®, Striverdi®, Spiolto®.
- By overall and type of re-usable Respimat® SMI product prescribed prior to study entry:
 - Duration of re-usable Respimat® SMI product prescribed prior to study entry (days) - calculated relative to signed ICF date.

For *Respimat® SMI-experienced patients on maintenance treatment with a disposable Respimat and switching to a re-usable Respimat® SMI at study entry* the following will be described:

Document:	\	.net\Enterprise\Sites\USCBG\Depts\BioStat\Boehringer\Documentation\SAP\Final	
Author:		Version Number:	1.0

Template No.: RWI_TP_BIOS0013 Revision 1

Reference: RWI_WI_BIOS0015

Effective Date: 15Jun2018

- Disposable Respimat® SMI product prescribed prior to study entry: Spiriva®, Striverdi®, Spiolto®.
- By overall and type of disposable Respimat® SMI product prescribed prior to study entry:
 - Duration of disposable Respimat® SMI product prescribed prior to study entry (days) - calculated relative to date of last use of disposable Respimat® SMI product.

Derivations:

- For *Respimat® SMI-experienced patients on maintenance treatment with a re-usable Respimat® SMI at study entry:*
 - *Duration of re-usable Respimat® SMI product prescribed prior to study entry (days) = [(date of signed ICF – date of first use of re-usable Respimat® SMI) + 1].*
- For *Respimat® SMI-experienced patients on maintenance treatment with a disposable Respimat and switching to a re-usable Respimat® SMI at study entry:*
 - *Duration of disposable Respimat® SMI product prescribed prior to study entry (days) = [(date of last use of disposable Respimat® SMI – date of first use of disposable Respimat® SMI) + 1].*

Details on conversion factors used for dates and on handling of partial dates of first and last use of re-usable Respimat® SMI are described in [Appendix 1](#) and [Appendix 2](#), respectively.

Supportive listing for previous Respimat® SMI use will be provided.

Document:	\	.net\Enterprise\Sites\USCBG\Depts\BioStat\Boehringer\Documentation\SAP\Final	
Author:		Version Number:	1.0

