- *Duration of non-Respimat® SMI maintenance product prescribed prior to study entry (days) = [(End date – Start date) + 1].*
- *Last non-Respimat® SMI maintenance product prescribed prior to study entry = non-Respimat® maintenance product prescribed prior to study entry where max (Start date) < date of signed ICF and End date < date of signed ICF.*
- *Last inhaler device used prior to study entry = inhaler device associated with the last non-Respimat® SMI maintenance product prescribed prior to study entry.*

Details on conversion factors used for dates and on handling of partial dates of start and end date of medications are described in [Appendix 1](#) and [Appendix 2](#), respectively.

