23.2 APPENDIX 2. Partial Date Conventions

Partial dates will be imputed as follows:

Previous and Concomitant Medications:

Incomplete dates for previous/concomitant medications will be imputed as follows:

- If the medication start date is missing completely, then the medication date will be replaced by the signed ICF date.
- If the day of medication start date is missing, but the month and year are equal to the signed ICF date, then the medication date will be replaced by the signed ICF date.
- If both the day and month of the medication start date are missing but the year is equal to the signed ICF year, then the medication start date will be replaced by the signed ICF date.
- In all other cases, the missing medication day or missing medication month will be replaced by 1.
- Incomplete medication stop date will be replaced by the last day of the month (if day is missing only), if not resulting in a date later than the date of the subject's death. In the latter case, the date of death will be used to impute the incomplete stop date.
- In all other cases, the incomplete medication stop date will not be imputed.

Disease History and Spirometry:

Incomplete dates for date of COPD diagnosis and date of last available spirometry assessment prior to study entry will be imputed as follows:

Document:	\	.net\Enterprise\Sites\USCBG\Depts\BioStat\Boehringer\Documentation\SAP\Final	
Author:		Version Number:	1.0

Template No.: RWI_TP_BIOS0013 Revision 1

Reference: RWI_WI_BIOS0015

Effective Date: 15Jun2018

- If the day is missing, it will be imputed to the 15th day of the month.
- If both day and month are missing and the year is prior to the year of the signed ICF date, the month and day will be imputed as July 1st.
- If both day and month are missing and the year is the same as the year of the signed ICF date, the month and day will be imputed as January 1st.
- If the date is completely missing, no imputation will be performed.

Exposure:

Incomplete and partial dates for date of first use of re-usable Respimat® SMI prior to study entry will be imputed as follows:

- If the day is missing, it will be imputed to the 15th day of the month.
- If both day and month are missing and the year is prior to the year of the signed ICF date, the month and day will be imputed as July 1st.
- If both day and month are missing and the year is the same as the year of the signed ICF date, the month and day will be imputed as January 1st.

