- If the date is completely missing, no imputation will be performed.

Incomplete and partial dates for date of first use and date of last use of disposable Respimat® SMI prior to study entry will be imputed as follows:

- If the day of first use of disposable Respimat® SMI date is missing, it will be imputed to the 15th day of the month.

Document: \\ .net\Enterprise\Sites\USCBG\Depts\BioStat\Boehringer\Documentation\SAP\Final

Author: Version Number: 1.0

Version Date: 100CT2019

Template No.: RWI_TP_BIOS0013 Revision 1

Reference: RWI_WI_BIOS0015

Effective Date: 15Jun2018

- If both day and month of first use of disposable Respimat® SMI date are missing but the first use year is prior to the year of the signed ICF date, the month and day will be imputed as July 1st.
- If both day and month of first use of disposable Respimat® SMI date are missing but the first use year is equal to the year of the signed ICF date, the month and day will be imputed as January 1st.
- If the disposable Respimat® SMI first use date is completely missing, no imputation will be performed.
- Incomplete disposable Respimat® SMI last use date will be replaced by the last day of the month (if day is missing only).
- If the disposable Respimat® SMI last use date is completely missing, it will be imputed by the signed ICF date.

Incomplete and partial dates for prescribed date of re-usable Respimat® SMI at study entry will be imputed as follows:

- If the day of prescribed date of re-usable Respimat® SMI at study entry is missing, but the month and year are equal to the dispensed date, then the prescribed date will be replaced by the dispensed date.
- If both day and month of prescribed date of re-usable Respimat® SMI at study entry are missing but the prescribed year is equal to the year of the dispensed date, then the prescribed date will be replaced by the dispensed date.
- In all other cases, the missing day of the prescribed date of re-usable Respimat® SMI at study entry will be replaced by 1.

Document: \\ .net\Enterprise\Sites\USCBG\Depts\BioStat\Boehringer\Documentation\SAP\Final

Author: Version Number: 1.0

Version Date: 100CT2019

Template No.: RWI_TP_BIOS0013 Revision 1

Reference: RWI_WI_BIOS0015

Effective Date: 15Jun2018

- If the prescribed date is missing, it will be imputed by the dispensed date. If the dispensed date is missing, prescribed date will be imputed by the signed ICF date.

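### SAP Appendix 2 treats start dates known only to the year inconsistently, so some descriptive durations are biased or impossible and a prior inhaler can drop out of the SMI-naïve subgroups

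*SAP*

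**What the plan says.** All the rules below are in SAP 23.2 (Appendix 2). ICF means the informed consent form, whose signature date is study entry.

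- **Last spirometry and first use of the re-usable Respimat.** A missing day becomes the 15th. Two rules cover a date recorded to the year alone. The earlier-year rule reads: "the year is prior to the year of the signed ICF date, the month and day will be imputed as July 1st". The ICF-year rule reads: "the year is the same as the year of the signed ICF date, the month and day will be imputed as January 1st".
- **First use of the disposable Respimat.** The same pattern applies, including the branch where "the first use year is equal to the year of the signed ICF date, the month and day will be imputed as January 1st".
- **Medications, which include the other maintenance inhalers.** A start recorded to the ICF year alone falls under this clause: "the year is equal to the signed ICF year, then the medication start date will be replaced by the signed ICF date". For earlier years: "In all other cases, the missing medication day or missing medication month will be replaced by 1".

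These dates feed four derivations:

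- time since spirometry (SAP 12.5)
- duration of prior Respimat use (SAP 17)
- duration of prior non-Respimat maintenance products (SAP 18)
- the last non-Respimat product and last device (SAP 18), which define two SMI-naïve subgroups in SAP 9.4.

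The SAP gives no reason for the different conventions.

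**The concern.** There are three separate problems.

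(a) For spirometry and Respimat use, the SAP takes a central date when the day is missing or the year is an earlier one. In the ICF year it takes the earliest possible day. No record in that branch can be understated, so the error runs one way.

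(b) A start known only as 2018 is placed on 1 July for a Respimat and on 1 January for any other inhaler.

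(c) A non-Respimat start known only to the ICF year is placed on the ICF date. If the patient stopped that product before consent, the imputed start falls after the stop.

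At stake are the baseline tables that describe how long patients had used their previous inhaler and how old their spirometry is. Problem (c) also affects which SMI-naïve patients enter the last-product and last-device subgroups, and those subgroups are applied to the PASAPQ outcomes.

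**Working it through.** The SAP states no figure for the size of this error, so there is none to reproduce. The check is date arithmetic.

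**Inputs.** Enrolment runs September to December 2019 (SAP 4.1); the protocol says from August (section 9.2.1). One month is 30.4375 days (SAP Appendix 1). Durations are end minus start plus 1 day (SAP 17, 18). Assumption, not in the documents: the true date is uniform over its possible interval.

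**(a) ICF year, 1 January rule.** Overstatement = true date - 1 January. Its mean is (ICF date - 1 January)/2 and its maximum is ICF date - 1 January.

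| ICF date | Days from 1 Jan | Mean overstatement | Single-patient range |
|---|---|---|---|
| 1 Sep 2019 | 243 | 121.5 days = 3.99 months | 0 to 7.98 months |
| 31 Oct 2019 | 303 | 151.5 days = 4.98 months | 0 to 9.95 months |
| 31 Dec 2019 | 364 | 182 days = 5.98 months | 0 to 11.96 months |

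With the protocol's August start, 1 August gives 212/2 = 106 days = 3.48 months.

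Sensitivity for September to December: a triangular distribution rising toward the ICF date has mean 2/3 of the span, or 5.32 to 7.97 months. One falling from 1 January has mean 1/3, or 2.66 to 3.99 months. The size depends on the assumption; the sign does not.

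For the disposable device the possible interval ends at last use, so these figures apply when last use is at about the ICF date and are smaller if it was earlier.

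The date of COPD diagnosis shares the spirometry rule but is harmless. COPD duration is reported in whole years, and (364 + 1)/365.25 = 0.999, which truncates to 0.

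**(b) Earlier year.** From 1 January to 1 July 2018 is 181 days. With true dates uniform over 2018, the mean overstatement is 364/2 = 182 days (5.98 months) for another inhaler and 182 - 181 = 1 day (0.03 month) for a Respimat.

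This branch matters only if SAP 18 counts products that began before its 6-month look-back. SAP 18 speaks of use in that window. SAP 16 defines previous medications as both started and stopped within it. Six months (183 days) before 1 September 2019 is 2 March 2019, so on the SAP 16 reading no 2018 start could occur.

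**(c) ICF year, other inhalers.** Imputed duration = stop date - ICF date + 1, which is zero or negative for any stop before the ICF date. Example: stop 31 August, ICF 15 October 2019 gives -45 + 1 = -44 days. The true value lies between 1 day (start 31 August) and 242 + 1 = 243 days (start 1 January).

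The last-product rule in SAP 18 requires the start to be earlier than the ICF date. An imputed start equal to the ICF date fails it. The derivation then falls back on an older product or on None, and SAP 9.4 runs no subgroup analysis on None.

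**The case against.** The case for leaving the text alone has five parts.

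- **The outputs are descriptive.** SAP 17 and 18 summarise the durations separately. No planned analysis contrasts them, and duration is not a subgroup variable in SAP 9.4. This stands. A reader might infer that the plan compares prior Respimat with prior non-Respimat duration and that this comparison is spoiled, but the documents plan no such comparison.
- **Imputation is made visible.** SAP 9.3 flags derived variables in listings, and SAP 9.2 reports median and quartiles beside the mean. This softens (a) and (b). It does not repair a negative duration or a lost subgroup member.
- **1 January is a safe convention.** It precedes consent and keeps ICF-year spirometry inside the 12-month window. That is true, but a midpoint between 1 January and the ICF date does both as well.
- **The bias is not uniformly upward.** A reader of (a) and (b) might conclude that all prior durations are inflated. They are not: (c) shortens non-Respimat durations.
- **The number of records is unknown.** A reader might multiply 4 to 6 months by a guessed share of year-only records to get a group-mean shift. The documents give no share, and year-only Respimat dates in earlier years carry almost no error, so such a figure has no basis.

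**Conclusion.** The point holds as a minor one.

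- For records with only the ICF year known, time since spirometry and prior Respimat duration are overstated by a mean of about 4 to 6 months. This assumes uniform true dates and consent from September to December 2019. Skewed dates give about 2.7 to 8.0 months.
- Earlier-year starts differ by 181 days between Respimat and other inhalers, provided SAP 18 counts products started before the look-back.
- Branch (c) is the most serious because it yields impossible durations and can remove a product from the last-product and last-device derivation.

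No group-level shift can be stated. The primary PASAPQ summary and the paired comparison in the full cohorts do not use these dates. The only route to an outcome table is membership of the two SMI-naïve subgroups, which SAP 9.4 calls exploratory.

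**What to change.** In Appendix 2:

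1. For spirometry and Respimat first use with only the ICF year known, impute the midpoint between 1 January and the signed ICF date. For the disposable Respimat, end the interval at the earlier of last use and the ICF date. Carrying over 1 July is not equivalent: for an ICF date of 1 September 2019 it is on average 181 - 121.5 = 59.5 days too late.
2. For the SAP 18 duration and last-product derivation only, impute a year-only non-Respimat start as 1 July for an earlier year. For the ICF year, use the midpoint between 1 January and the earlier of the stop date and the ICF date. Never impute a start after a known stop date. In the example above the start becomes 2 May 2019 and the duration 242 - 121 + 1 = 122 days.
3. Keep the existing medication rules for the previous/concomitant classification.
4. State in SAP 18 whether products started before the 6-month window count, and reconcile this with SAP 16.

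The cost is a few lines of SAP wording and code before database lock. No new data are needed, and the full-cohort PASAPQ results do not change.

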**Exclusion criteria:**

Patients fulfilling any of the following exclusion criteria will not be eligible for participation in the study:

- Patient using a disposable Respimat SMI product during the study period, after study entry
- Patient who have had a severe COPD exacerbation requiring hospitalisation in the immediate 3 months prior to study entry
- Patient participating in a clinical trial or any other non-interventional study of a drug or inhaler at the time of enrolment
- Visual, cognitive, motor or health impairment that, as judged by the investigator, may cause concern regarding the patient's ability to complete the questionnaires
- Patient not fluent and literate in one of the main languages of the country

Where allowed by local regulations, a patient screening log will be kept at each site, recording basic information such as age at COPD diagnosis, gender, information on the eligibility (or reasons for non-eligibility/non-enrolment, including a reason for refusal [if known]). In addition, a log of all patients included into the study (i.e. having provided informed consent) will be maintained in the Investigator Site File irrespective of whether they have completed the study or not.

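### SAP Appendix 2 does not cap imputed pre-entry dates at the consent date, so some derived durations are overstated or negative

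*SAP*

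**What the plan says.** SAP section 8.4 makes the visit at which consent is signed the baseline, that is, study entry. SAP Appendix 2 (section 23.2) then gives rules for incomplete dates.

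- **Disposable inhaler.** The rules are introduced with the words "date of last use of disposable Respimat® SMI prior to study entry will be imputed as follows". For last use with only the day unknown: "Incomplete disposable Respimat® SMI last use date will be replaced by the last day of the month (if day is missing only". For last use with nothing known: "If the disposable Respimat® SMI last use date is completely missing, it will be imputed by the signed ICF date". A first use date without its day goes to the 15th.
- **Spirometry and diagnosis.** The introduction reads "Incomplete dates for date of COPD diagnosis and date of last available spirometry assessment prior to study entry will be imputed as follows", and the rule is "If the day is missing, it will be imputed to the 15th day of the month".
- **First use of the re-usable inhaler before entry.** The same 15th-of-month rule applies.
- **Medications.** Here the boundary is handled. For a start date the rule opens "If the day of medication start date is missing, but the month and year are equal to the signed ICF date", and the date is then set to the consent date. A stop date goes to month-end only "if not resulting in a date later than the date of the subject's death".

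The derived variables are COPD duration (SAP 12.2), time since spirometry (SAP 12.5), and duration of prior disposable or re-usable use (SAP 17). None of these sections caps the input dates or says what to do with a negative result.

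**The concern.** The rules are written for events before study entry, but they can return dates after it. This matters most for last disposable use. Patients in subgroup 1b switch at study entry, so the consent month is the natural month for their last use. If the day is unknown, month-end lies after consent unless consent was signed on the last day of the month. A patient with no date at all is given the consent date, so knowing the month produces a less plausible value than knowing nothing.

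The 15th rule fails differently. If consent was early in the month, the 15th is still ahead, and an interval counted back from consent becomes zero or negative. At stake are the accuracy and face validity of the exposure and baseline tables: disposable durations that run on past entry, and negative times since spirometry.

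**Working it through.** The plan states no figure here to reproduce. The check applies its rules to each possible consent date.

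**Inputs**
- Entry is the consent date (SAP 8.4).
- Consent dates run from 1 September to 31 December 2019 (enrolment window in SAP 4.1): 30 + 31 + 30 + 31 = 122 days.
- The day is missing and the known month is the consent month.
- Derivations (SAP 12.5 and 17): time since spirometry = (consent - spirometry + 1) / 30.4375 months; prior re-usable duration = consent - first use + 1 days; disposable duration = last use - first use + 1 days.

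**Last disposable use at month-end**
- Overshoot = last day of the month - day of consent. It is zero on one date per month, so last use falls after entry on 122 - 4 = 118 of 122 dates (96.7%).
- The maximum is 31 - 1 = 30 days. The mean is (2 × 435 + 2 × 465) / 122 = 1800 / 122 = 14.8 days.
- Example: consent on 3 October 2019 with last use known only as October gives 31 October, and 31 - 3 = 28 days after entry. Follow-up itself is only 4 to 6 weeks.
- Disposable duration rises day for day with the imputed last use, so it is overstated by up to 30 days. This rule does not make it negative.

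**Spirometry or first re-usable use on the 15th**
- Interval in days = day of consent - 15 + 1 = day of consent - 14.
- It is negative for consent on days 1 to 13: 13 × 4 = 52 of 122 dates (42.6%). It is zero on day 14 (4 dates).
- The minimum is 1 - 14 = -13 days; for spirometry, -13 / 30.4375 = -0.43 months. Consent on 3 October gives -11 days, or -0.36 months.

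**COPD diagnosis on the 15th**
- The raw interval is the same, and -13 / 365.25 = -0.036 years. The SAP reports the integer part, which is 0 if truncated towards zero and -1 only if programmed as a floor. Age at diagnosis uses calendar years only.

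**First disposable use against last use**
- First use imputed to 15 October with a known last use of 8 October gives 8 - 15 + 1 = -6 days. A cap at consent does not cure this if consent was, say, on 20 October.

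**Sensitivity to the window**
- Weekdays only: 84 of 87 dates for last use and 38 of 87 for negative spirometry time.
- Protocol 9.2.1 starts enrolment in August. Adding its 31 days gives (118 + 30) / (122 + 31) = 148 of 153, and (52 + 13) / 153 = 65 of 153. The proportions barely move.

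**Where only the year is known**
- For spirometry, diagnosis and first use, the current year becomes 1 January and an earlier year becomes 1 July. Neither passes consent.

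**After the fix**
- With the earlier of imputed date and consent date, the maximum overshoot is 0 days and the smallest interval from the 15th rule is +1 day.

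**The case against.** The best defence is that this is a programming detail with little reach. The introductory wording already limits most of these dates to the time before entry, so the intended bound is clear. The problem needs a missing day and a known month equal to the consent month. Last disposable use is recorded at the baseline visit (Protocol Table 1), when a recent event should be easy to date. The dry run and data review meeting before lock (SAP 5.2) offer a chance to notice a negative minimum.

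Much of this stands. The documents give no rate of partial dates, and 118 of 122 is conditional on such a date, not a prevalence. But a heading that states the intended bound does not enforce it, and the rule as written returns values outside it. Detection is also harder than it sounds: under SAP 9.3, listings omit imputed values and only flag the variables derived from them. A reviewer would see a flagged negative time without the date behind it.

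A reader might go further and infer that an imputed post-entry date breaches the exclusion "Patient using a disposable Respimat SMI product during the study period, after study entry" and so removes the patient from the FAS, which requires all eligibility criteria to be met (SAP 7.1). The documents do not support that. Eligibility is checked at baseline from medical records (Protocol Table 1 and 9.4.1). Inhaler type after entry is captured by a separate follow-up question (Protocol 9.4.1.1, SAP 19). Nothing judges eligibility from an imputed date or sends imputations back to sites as queries.

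**Conclusion.** The point holds as a minor defect in a stated rule. For a date lacking its day in the consent month, last disposable use is placed after entry on nearly every possible consent date, by up to 30 days. Time since spirometry and prior re-usable duration are negative for consent on days 1 to 13, down to -13 days. The effect on COPD duration is negligible. These results assume that the rules are programmed literally and that consent dates fall in the stated window. How many patients are affected cannot be estimated from the documents.

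It would be tempting to read this as a threat to the baseline-to-end comparison in subgroup 1b. It is not shown to be one. The three paired comparisons in SAP 20.2.1.4 (total, performance and convenience) use questionnaire scores only, as does the primary outcome. None of the affected durations defines a subgroup in SAP 9.4. The consequence is limited to descriptive baseline and exposure summaries.

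**What to change.** Add two rules to SAP Appendix 2:

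1. Any imputed date of last disposable use, first disposable or re-usable use, spirometry or COPD diagnosis that falls after the signed consent date is set to the consent date.
2. An imputed first disposable use date may not be later than the last use date.

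The second rule is needed because the cap alone leaves cases such as the -6 days shown above. The cost is two sentences in the SAP and a minimum function in the derivation programs. No data collection, outcome analysis or sample size changes.

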8.4 Baseline Visit

The routine visit, at which a patient is enrolled in the study (time of ICF signature), will be treated as the baseline (study entry) visit.

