8.6 Study Observation Period

The study observation period will start on the date of signed ICF (study enrolment date) until the end of study date (see [Section 8.5](#)). The study duration (days) will be calculated as follows:

$$\text{Study duration (days)} = [(End \text{ of study date} - date \text{ of signed ICF}) + 1]$$

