19. RE-USABLE RESPIMAT® SMI PRESCRIPTION

Analysis Set: FAS

Re-usable Respimat® prescription data will be collected under the “Respimat® Exposure” eCRF page. The prescription at study entry of each type of re-usable Respimat® SMI product will be analysed overall and by patient cohort. The following will be described overall and for each type of re-usable Respimat® SMI product prescribed at study entry:

- Duration of use of re-usable Respimat® SMI product during the study period (days) - calculated relative to prescribed date.
- Pack type: Cartridges only, Inhaler and cartridges.
- Pack size: 30 days (1 month), 90 days (3 months).

Document:	\	.net\Enterprise\Sites\USCBG\Depts\BioStat\Boehringer\Documentation\SAP\Final
Author:		Version Number: 1.0

Template No.: RWI_TP_BIOS0013 Revision 1 Reference: RWI_WI_BIOS0015

Effective Date: 15Jun2018

Additionally, at the time of the follow-up assessment, a single question will be asked to all patients to confirm the use of a re-usable version of Respimat® SMI during the study period as follows:

- What type of inhaler have you been using since commencing the study?: Re-usable inhaler, Disposable inhaler.

Derivations:

- Duration of re-usable Respimat® SMI product prescribed at study entry (days) = $[(\text{End of study date} - \text{Prescribed date}) + 1]$.

Details on conversion factors used for dates and on handling of partial dispensed date of reusable Respimat® SMI are described in [Appendix 1](#) and [Appendix 2](#), respectively.

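### When only the day of the study-entry prescribed date is missing and dispensing falls in another month, SAP Appendix 2 can place the prescription before consent, so the derived duration of use exceeds the study period

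*SAP*

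**What the plan says.** SAP Appendix 2 (Exposure) handles a partial prescribed date of the re-usable device at study entry in this order:

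- If only the day is missing and the "month and year are equal to the dispensed date, then the prescribed date will be replaced by the dispensed date".
- If day and month are missing, the dispensed date is used when the years agree.
- "In all other cases, the missing day of the prescribed date of re-usable Respimat® SMI at study entry will be replaced by 1".
- "If the prescribed date is missing, it will be imputed by the dispensed date". The same bullet continues: "If the dispensed date is missing, prescribed date will be imputed by the signed ICF date".

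Three other places bear on this. SAP 8.4 fixes study entry: "The routine visit, at which a patient is enrolled in the study (time of ICF signature), will be treated as the baseline (study entry) visit". SAP 8.6 defines the study window: "The study observation period will start on the date of signed ICF (study enrolment date) until the end of study date". SAP 19 lists the affected variable: "Duration of use of re-usable Respimat® SMI product during the study period (days) - calculated relative to prescribed date", derived as end of study date minus prescribed date plus 1.

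Protocol 9.1 and SAP 4.1 say that both cohorts receive the re-usable prescription at study entry.

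**The concern.** A prescription made at study entry has a nearly known date. If the recorded month and year match the ICF, the ICF date is the natural estimate. The residual line instead uses the first of the month, which precedes study entry for every ICF date except the 1st.

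The same appendix already has the right convention. A medication start date with a missing day takes the ICF date when its month and year match the ICF. The prescribed-date rules have no counterpart.

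What is at stake is the credibility of one exposure summary. A duration labelled as falling within the study period should not exceed that period, and here the stated rule can make it do so.

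**Working it through.** The documents give no figure to reproduce, so the check is date arithmetic on the SAP's own rules.

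**Inputs**
- Study duration = end of study date − ICF date + 1 (SAP 8.6).
- Duration of use = end of study date − prescribed date + 1 (SAP 19).
- Follow-up of about 4 to 6 weeks, taken as 28 and 42 days (SAP 4.2).
- Enrolment from September to December 2019 (SAP 4.1): 30 + 31 + 30 + 31 = 122 ICF dates.
- Assumption: the prescription is written on the ICF date, as its description as a study-entry prescription implies.
- Assumption: dispensing follows 1 to 7 days later. The documents give no lag, so 14 days is also shown.

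**Step 1: excess per affected patient.** Excess = duration of use − study duration = ICF date − imputed prescribed date. With the prescribed month equal to the ICF month and day 1 imputed, this is ICF day of month − 1. The maximum is 31 − 1 = 30 days (ICF on 31 October or 31 December), or 29 days in a 30-day month.

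**Step 2: which ICF dates can trigger it.** Dispensing must fall in the next month. With a lag of L days, that means the last L days of each of four months, so 4 × L dates.

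| Assumed lag (days) | ICF dates out of 122 | Excess (days) |
|---|---|---|
| 1 | 4 (3%) | 29–30 |
| 3 | 12 (10%) | 27–30 |
| 7 | 28 (23%) | 23–30 |
| 14 | 56 (46%) | 16–30 |

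These are dates on which the rule could apply. A patient is affected only if the day of the prescribed date is also missing.

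**Step 3: against the study period.** Study duration is 28 + 1 = 29 to 42 + 1 = 43 days. For lags of 1 to 7 days, the excess runs from 23/43 = 53% to 30/29 = 103% of it.

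**Step 4: examples**
- ICF 25 October, prescribed October 2019 with no day, dispensed 2 November. The prescribed date becomes 1 October, 24 days early. Duration of use is 29 + 24 = 53 days at 28-day follow-up and 43 + 24 = 67 days at 42-day follow-up, instead of 29 and 43. The lag here is 8 days, but any November dispensing date gives the same result.
- ICF 31 October, dispensed in November: 59 days instead of 29, or 73 instead of 43.

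**Step 5: effect on the summary.** One affected patient among about 250 moves the mean by 23/250 = 0.09 to 30/250 = 0.12 days. The reported maximum is more exposed, since a single case can set it.

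**Step 6: after the change proposed below.** The imputed date is the ICF date, the excess is 0, and the durations return to 29 and 43 days.

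**The case against.** The strongest case against acting is that this should hardly ever happen. The prescription is issued at the enrolment visit, so a missing day should be unusual, and dispensing must also fall in another month. Protocol 9.6 provides eCRF edit checks for missing or illogical data. SAP 5.2 plans a dry run and a data review meeting before lock, and SAP 9.3 flags variables derived from imputed values in listings. All of this stands and keeps the point minor. It does not remove the point: the SAP wrote rules for partial prescribed dates because it expected some, and the flag appears in listings while the value still enters the summary table.

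Three stronger readings are tempting, and the documents do not support them.

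- **That most ICF dates are exposed.** Averaged over all 122 ICF dates, the shift would be 14.8 days on average and non-zero on 118 dates (97%). Those figures describe a missing dispensed date, where the outcome is not settled. The sentence "If the dispensed date is missing, prescribed date will be imputed by the signed ICF date" follows the one on a missing prescribed date and most naturally continues it, which would leave a day-missing date to the residual line. Read as a stand-alone rule, it gives the ICF date and no shift. That is an ambiguity to resolve, not a demonstrated error.
- **That knowing the month is handled worse than knowing nothing.** A wholly missing prescribed date takes the dispensed date first, and the ICF date only if that is missing too. The contrast depends on the same contested sentence.
- **That the added days precede any use of the device.** Subgroup 1a is already on a re-usable Respimat at study entry. For these patients the valid complaint is only that a duration within the study period exceeds that period.

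**Conclusion.** The point holds in a narrow form. When the day is missing, the prescribed month is the ICF month and dispensing falls in the following month, the SAP unambiguously assigns a date before study entry and a duration of use longer than the study duration. For lags of 1 to 7 days the excess is 23 to 30 days on 29 to 43, and it can arise on 4 to 28 of 122 ICF dates, near month end.

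This rests on the prescription being written on the ICF date and on the assumed lag. If it was written a little earlier, day 1 is less wrong as a date, but the duration still cannot properly exceed the period it is said to cover. The documents give no rate of day-missing prescribed dates, and the number affected is probably very small.

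Only a descriptive exposure summary is touched. The PASAPQ scores, the paired change, the preference question, FAS membership and the planned subgroups do not use this duration, and study duration is reported separately from the ICF date (SAP 11). This is a minor correction.

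**What to change.** Keep the residual line and insert a rule before it, modelled on the medication start-date rule: *Where the day, or the day and month, of the prescribed date is missing, the parts that are known agree with the signed ICF date, and the dispensed-date rules above do not yield a complete date, use the signed ICF date.*

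Then:
- State that the ICF fallback in the last bullet also covers a partial prescribed date whose known parts agree with the ICF date, when the dispensed date is missing or partial. This settles the ambiguity.
- Raise a query when the recorded prescribed month conflicts with the ICF date. A blanket floor at the ICF date would be wrong, because it would override a recorded earlier month (for example, prescribed in September with ICF on 3 October). Deleting the residual line would leave non-matching months with no rule.
- As a separate tidy-up, SAP 19 refers to Appendix 2 for a partial dispensed date, but the appendix has no such rule. Add one or drop the reference.

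The cost is a few lines of SAP wording and one added condition in the derivation code, before database lock. No new data are needed.
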